### **Study Protocol**

#### Trial Design

In a 3-arm, parallel-group, assessor-blinded, stratified-randomized trial, participants were enrolled based on the following eligibility criteria: aged 18 years or older, having received at least one dose of the COVID-19 vaccine but no doses since September 11, 2023, and no SARS-CoV-2 infection in the three months prior to the study start. We focused on individuals with at least one prior dose—the "moveable middle"—who show some willingness to vaccinate but remain hesitant about additional doses and may be more responsive to a brief video intervention than the unvaccinated. Our team's prior research informed the trial design, and identified safety and efficacy as their main concerns.

Eligible individuals were randomly allocated to one of three interventions: 1) attitudinal inoculation, 2) CBT-kernels or 3) standard public health messaging. Recruitment and randomization started on April 15, 2024 and continued on a rolling basis until May 02, 2024. Outcome assessment at 4-week follow-up started on May 13, 2024 and was completed by June 13, 2024. After consenting, enrolled participants were randomly assigned to one of three arms at a ratio of 1:1:1. Each arm was also stratified by presence or absence of moderate to severe anxiety or depression symptoms, defined by scoring  $\geq$ 10 in the Patient Health Questionnaire-8 or GAD-7 at any point between December 2022 and December 2023.

#### Recruitment

Individuals were recruited from the CHASING COVID cohort, a well-characterized, community-based sample of geographically and socio-demographically diverse adults aged 18 years and older who reside in the US or US territories and enrolled in the cohort between March 28, 2020 and August 21, 2020. Details of recruitment and follow-up have been described elsewhere. Briefly, participants in the cohort have completed, approximately quarterly, online assessments related to health and behaviors, SARS-Cov-2 infection history, COVID-19 symptoms, and COVID-19 vaccination status.

#### **Informed Consent**

The study received approval from the Institutional Review Boards of the City University Of New York (CUNY) Graduate School of Public Health and Health Policy (New York, NY, USA) (protocol NCT06119854) and followed the Consolidated Standards of Reporting Trials (CONSORT) social and psychological interventions (SPI) reporting guidelines. Informed consent forms were completed via web browser on participants' computers or mobile devices at baseline and periodic follow-up assessments. The trial was pre-registered at: https://clinicaltrials.gov/study/NCT06119854

#### **Participants**

Participant eligibility criteria at the time of study enrollment (April-June 2024) were as follows: (1) aged 18 and older, (2) able to read in English, (3) current residence in the US, (4) completed at least one survey as part of the CHASING COVID Cohort study between December 7, 2022 and December 22, 2023, and (5) undervaccinated, defined as having received at least one dose of

the COVID-19 vaccine, but not an updated COVID-19 vaccine dose since September 11, 2023. Participants were excluded if they (1) had a SARS-CoV-2 infection in the past three months, (2) had never received *any* dose of a COVID-19 vaccine, or (3) were flagged for fraudulent behavior. Fraudulent participants were identified as showing evidence of duplicate or inconsistent contact information, suspicious response times, repeated enrolment attempts, or fraudulent flags raised from other CHASING COVID-based studies. Further details of participant characteristics can be found in Appendix A.

Intervention delivery and data collection occurred fully online. Participants completed an online survey at enrollment and at 4-weeks following enrollment.

### **Intervention and Control Conditions**

Participants viewed one of three one-minute videos. The video content of the experimental arms was developed using formative mixed-methods research, including a pre-trial survey with CHASING COVID participants on vaccine perceptions and qualitative interviews with participants reporting anxiety or depression in earlier questionnaires. This process revealed a common concern about vaccine effectiveness as a broader "meta-narrative" across participants. Additionally, those with anxiety or depressive symptoms were more likely to cite not "making time" as a reason for being behind on vaccination- a theme later incorporated into the CBT-kernels condition.

Specifically: 1) The inoculation video addressed concerns about vaccine effectiveness, focused on bolstering resistance to mis/disinformation. 2) The CBT-kernels video focused on addressing barriers to vaccination, specifically making time to get vaccinated. It focused on cognitive reframing—highlighting how individuals might selectively focus on information that reinforces vaccine-related anxiety, challenging those beliefs, and encouraging problem-solving around making time to get vaccinated. 3) The standard public health messaging arm was a brief video adapted from existing public health PSAs, with no inoculation or CBT-kernels elements.

The videos were professionally created in collaboration with Long Story Short, a production company with experience in PSA creation that has worked with local, national, and global public health organizations. Our research team worked closely with the production team throughout the process, iterating on scripts, refining takes, selecting actors, and providing detailed feedback to ensure clarity and consistency. The research team included experts in mental health disorders, COVID-19 surveillance, infection and transmission, vaccine hesitancy and uptake, public health emergency preparedness and response, and risk communication. A member of the research team was present on set during filming to oversee production and ensure fidelity to our intended messaging. By creating all videos within the same production process, we maintained control over factors such as tone, format, duration, and overall presentation, reducing the risk of unintended differences that could influence participants' responses. This approach allowed us to isolate the effects of the different messaging strategies while ensuring that all videos were aligned in terms of quality and delivery. A description and scripts of these videos can be found in Appendix D.

## Attitudinal inoculation to increase vaccination among adults with anxiety or depression RF1MH132360

### Study Protocol and Statistical Analysis Plan May 2, 2025

After receiving the brief digital intervention, participants received two reminders to get vaccinated by text or email on the first and third days after completing the baseline assessment. Messages were tailored to each arm and included a link to a COVID-19 vaccine locator. Their content can be found in Appendix A.

### Stratified Randomization Procedure and Masking

#### Sequence Generation

We used a two-stage procedure for randomization. First, participants eligible for recruitment were stratified into two groups based on the presence or absence of symptoms of anxiety or depression reported at any point between December 2022 and December 2023. Second, participants in both strata were randomized to one of the three intervention arms upon being enrolled. Thus, participants were randomized separately according to symptoms of anxiety or depression.

#### Measures

#### Intervention Implementation (Adherence) Measure

The survey was programmed to require participants to remain on the video page for at least the duration of the video. However, time spent on the webpage doesn't necessarily reflect attentiveness, hence participants were also asked "Did this video hold your attention?" with options "Yes, it held my attention" and "No, it did not hold my attention / I did not watch the video."

#### Primary Outcome: Receipt of COVID-19 Vaccine Dose at 4 Weeks

At the 4-week survey, participants were asked, "Have you received a COVID-19 vaccine dose since {date of intervention}?" Participants who responded "yes" were considered vaccinated; otherwise, they were not.

#### Secondary Outcome: Vaccine Willingness at 4 Weeks

At the 4-week survey, participants who had not received an additional dose of the vaccine were asked, "How willing are you to receive another COVID-19 vaccine dose?" with response options: "Very willing", "Somewhat willing", "Not willing", or "Don't know". Only participants who responded 'Very willing' were defined as vaccine willing.

Pre-trial vaccine willingness. After enrollment, but before randomization into an intervention arm, participants were asked, "How willing are you to receive another COVID-19 vaccine dose?" with response options: "Very willing", "Somewhat willing", "Not willing", or "Don't know".

Post-trial vaccine willingness: Immediately after the intervention, participants were asked: "How likely are you to make time to get a vaccine in the next month?" with response options: "Very likely," "Somewhat likely," "Not likely," and "Don't know/not sure." They were also asked:

"Are you planning to make an appointment to get the COVID-19 vaccine in the next month?" with options: "Already made an appointment", "Planning", "Not planning", "Don't know/not sure". These questions were asked again in the 4-week follow-up survey, but only among participants who had not received an additional vaccine dose during that time. For participants with missing follow-up data (N=56), responses from the immediate post-intervention survey were used as imputed values.

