### Statistical Analysis Plan

All statistical analyses were performed blind to study arm allocation. We present frequencies and summaries of characteristics by treatment assignment. Standardized mean differences (SMD) were reported. For post-randomization characters, Chi-squared or Fisher's exact tests were used to compare proportions.

Primary analyses were performed under the intention-to-treat principle, including all participants who underwent randomization. Strict intention-to-treat analysis is hard to achieve for two reasons: missing outcomes for participants and protocol non-adherence. For the primary analysis, we used multiple imputation for those lost to follow-up at some point after randomization (as recommended by the CONSORT statement), which has the benefit of including all randomized participants. As a sensitivity analysis, we assessed loss to follow-up assumptions under (1) multiple imputation and (2) protocol non-adherence (see Appendix).

For the primary outcome, we generated risk ratios using a robust Poisson regression model and generated risk differences. For the secondary outcome of vaccine willingness, we generated risk ratios using a Poisson regression model. The model for the overall effect estimation included the randomization arms and a term for the presence or absence of symptoms of anxiety or depression reported between December 2022 and December 2023. For an Intention to Treat (ITT) analysis of a stratified randomized trial, adjustment is recommended for the stratification variable  on the principle that the analysis should follow the design.

To assess the effect of the intervention according to symptoms of anxiety or depression, we restricted them to subsets with or without symptoms. The stratified models included only randomization arms as the independent variable. Similarly, post-hoc stratification analyses for the primary and secondary outcomes were conducted separately among subsets of participants based on the presence or absence of the post-hoc stratification factors (susceptibility to severe

COVID-19, worry about COVID-19 and pre-trial perceptions of vaccine efficacy). The model included randomization arms and accounted for the presence or absence of symptoms of anxiety or depression.

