Lastly, the validity of an ITT effect estimate requires correct adjustment for selection bias due to differential loss-to-follow-up and missing outcome data. We used multiple imputation for loss-to-follow-up and missing data, hence conducting stratified analyses to assess effect modification rather than relying on interaction terms, as standard interaction testing isn't directly applicable to imputed datasets. Details on imputation methods are included in Appendix C. Methods for sensitivity analyses can be found in Appendix B. A series of sensitivity analyses were conducted to address assumptions related to loss to follow-up and protocol adherence, including complete case analysis, inverse probability weighting, perprotocol analysis for participants fully adhering to the intervention, and multiple imputation for missing outcomes, with consistent results observed across primary and secondary outcomes.

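### On its natural reading, the 4-week willingness risk ratio compares only participants who stayed unvaccinated, so it conditions on the primary outcome and is not a randomised comparison

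*Combined protocol and SAP*

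**What the plan says.** The combined protocol and SAP, under Secondary Outcome: Vaccine Willingness at 4 Weeks, restricts the question: "At the 4-week survey, participants who had not received an additional dose of the vaccine were asked" how willing they were to have another dose. It then sets the event: "Only participants who responded 'Very willing' were defined as vaccine willing". Whether a participant has had a dose since the intervention is asked in the same survey and is itself the trial's "Primary Outcome: Receipt of COVID-19 Vaccine Dose at 4 Weeks".

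The Statistical Analysis Plan section gives the model: "For the secondary outcome of vaccine willingness, we generated risk ratios using a Poisson regression model". The overall model holds arm and the symptom stratum. No denominator is given for willingness, and no code for a respondent who was not asked.

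Three other statements might have filled the gap:

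- **Analysis set.** The SAP describes analyses "including all participants who underwent randomization", but that sentence is about the primary analyses.
- **Multiple imputation.** It is first described for people lost to follow-up, and later more widely: "We used multiple imputation for loss-to-follow-up and missing data". The section adds that "Details on imputation methods are included in Appendix C".
- **Carry-forward.** "For participants with missing follow-up data (N=56), responses from the immediate post-intervention survey were used as imputed values". This follows the make-time and appointment items and concerns missing follow-up. No immediate post-video version of the willingness question is described.

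None of these mentions a respondent who skipped the willingness question because of a new dose. Appendices A to C are cited but were not available for this review.

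**The concern.** The primary outcome decides who has a value on the secondary outcome. If vaccinated respondents drop out of the willingness analysis, the groups compared are those who remained unvaccinated in each arm. Randomisation balanced the arms as allocated; it did not balance these subsets.

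Two things can then move the ratio without any difference in underlying willingness. One is a difference in uptake between arms, when vaccinees are not typical of everyone else. The other is a difference between arms in the kind of person who gets vaccinated. The second is plausible because, according to the section on intervention and control conditions, the videos address different barriers: effectiveness concerns in one, making time in another.

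At stake is the interpretation of the secondary outcome, overall and in the symptom-stratum and post-hoc subset analyses. A gain on vaccination could sit beside an apparent loss on willingness that only reflects willing people having acted. The primary outcome is not affected.

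**Working it through.** The documents state no uptake rate, willingness rate or sample size, so there is no figure of the plan's own to reproduce. Every rate below is an assumption.

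**Notation.** L is latent willingness: the share who would answer Very willing if nobody had been vaccinated, set equal in both arms so that the true risk ratio (RR) is 1.00. v0 and v1 are uptake in the control and active arms. q is the share of vaccinees who would otherwise have answered Very willing.

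**Step 1: vaccinated participants excluded.** The rate in an arm is (L − q·v)/(1 − v), so

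RR = [(L − q·v1)/(1 − v1)] / [(L − q·v0)/(1 − v0)].

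For L = 20%, q = 1:

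- 1% vs 2%: (0.18/0.98)/(0.19/0.99) = 0.1837/0.1919 = 0.96
- 2% vs 5%: (0.15/0.95)/(0.18/0.98) = 0.1579/0.1837 = 0.86
- 5% vs 10%: (0.10/0.90)/(0.15/0.95) = 0.1111/0.1579 = 0.70

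**Step 2: vary the assumptions, with q the same in both arms.**

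| L | q | 1% vs 2% | 2% vs 5% | 5% vs 10% |
|---|---|---|---|---|
| 20% | 1 | 0.96 | 0.86 | 0.70 |
| 20% | 0.5 | 0.98 | 0.95 | 0.90 |
| 40% | 1 | 0.98 | 0.95 | 0.90 |
| any | q = L | 1.00 | 1.00 | 1.00 |
| any | 0 | 1.01 | 1.03 | 1.06 |

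At q = L the rate reduces to L in each arm. At q = 0 the ratio is (1 − v0)/(1 − v1), for example 0.95/0.90 = 1.06. The shift grows as L falls: at L = 10%, q = 1 and 1% vs 2%, it is (0.08/0.98)/(0.09/0.99) = 0.90.

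**Step 3: equal uptake, different vaccinees.** With 5% uptake in both arms and L = 20%, q = 0.5 in control and 1 in active gives 0.15/0.175 = 0.86. The reverse gives 0.175/0.15 = 1.17.

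**Step 4: the same mechanism in counts.** Assume 200 per arm. Control has 4 vaccinated and 40 unvaccinated people answering Very willing. In the active arm 6 of those willing people get the dose, so it has 10 vaccinated and 34 very willing. Among the unvaccinated, 34/190 = 17.9% against 40/196 = 20.4%, RR 0.88, although vaccination rose 2.5-fold. Counting a dose or a Very willing answer as success gives 44/200 in both arms, RR 1.00.

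**Step 5: the composite.** Its rate is L + (1 − q)·v. At q = 1 the RR is 1.00 at every uptake pair. At L = 20%, q = 0.5 it is 0.210/0.205 = 1.02, 0.225/0.210 = 1.07 and 0.250/0.225 = 1.11. On the log scale it lies nearer to 1.00 than exclusion does only when q exceeds about 0.51 to 0.58 at L = 20%, or 0.66 to 0.69 at L = 40%. In the equal-uptake cases of Step 3 it gives 0.200/0.225 = 0.89 and 0.225/0.200 = 1.13.

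**The case against.** **The rule may be in Appendix C.** This stands. The SAP sends imputation detail there, so the point is a gap in the available text and not proof that no rule was written. If imputation of missing data does cover skipped questions, the problem shrinks only as far as the model recovers the willingness gap between vaccinated and unvaccinated. Imputing vaccinees as if they resembled the unvaccinated in their arm reproduces the exclusion ratio in expectation. Recovering half the gap gives 0.98, 0.93 and 0.87 at L = 20%, q = 1.

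**Willingness among the still unvaccinated is a sensible quantity.** As a description, yes. The ratio between arms is still not a randomised contrast and needs that label.

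**Direction and size are assumed.** This stands in full. A fall below 1.00 under exclusion with equal q requires q above L. That is plausible, but the documents do not state it. The 0.70 result needs 10% uptake in four weeks among people with no dose since September 11, 2023, all of them otherwise very willing.

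**A stronger reading: vaccinated people are scored as not willing.** A reader might infer this because only a Very willing response counts as an event; the ratios at L = 20%, q = 1 would then be 0.95, 0.83 and 0.67. The documents do not support it. The event definition follows a sentence that limits the question to people without a dose, nothing says that a person who was not asked counts as a failure, and the all-randomised wording concerns the primary analyses.

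**The composite has its own bias.** This also stands (Step 5), and it is why the composite cannot replace the existing analysis.

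**Conclusion.** The point holds for the text available. Being asked about willingness depends on the primary outcome, no stated rule covers respondents skipped because they were vaccinated, and the natural reading is a comparison within a subset formed after randomisation. This is more than a missing detail, because it changes what the willingness ratio can show.

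The size cannot be computed from the documents. On the assumed rates with equal q it runs from nothing (q = L), through a slight reversal (1.01 to 1.06 at q = 0), to 0.86 at 2% versus 5% uptake and 0.70 at 5% versus 10%, both with L = 20% and q = 1. Low uptake does not guarantee a negligible shift: at 1% versus 2% it is 0.96 with L = 20% but 0.90 with L = 10%.

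A reader might go further and conclude that the active arms' willingness results are biased downwards, or that the trial's main result is compromised. Neither follows. The direction depends on who was vaccinated in each arm, and the primary outcome does not use the willingness item.

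**What to change.** 1. State in the SAP how participants vaccinated by week 4 enter the willingness analysis, and report the denominators by arm. If Appendix C already gives the rule, repeat it beside the outcome definition.
2. Label willingness among the unvaccinated, overall and in subsets, as conditional on a post-randomisation outcome and not a randomised comparison.
3. Add beside it, for all randomised participants, the outcome of a dose since the intervention or a Very willing answer at 4 weeks. Use robust Poisson with the symptom-stratum term and the plan's multiple imputation for those lost to follow-up. Mark it as added after follow-up, which ended on June 13, 2024; the plan is dated May 2, 2025.
4. State the composite's limits with the result: it overlaps the primary outcome, measures acceptance more than attitude, and favours the higher-uptake arm when vaccinees were not all very willing. Show both versions.

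The cost is a few sentences, one derived variable and one table row, all from data already collected. Reconciling the carry-forward for the 56 participants with the multiple imputation is a separate matter.

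### The 4-week willingness outcome scores only *Very willing* in the not-yet-vaccinated and ignores pre-trial willingness; a supportive ordered analysis would cover what the cut cannot register

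*Combined protocol and SAP*

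**What the plan says.** The section on the secondary outcome gives three graded answers and a *Don't know* option, then sets the cut: "Only participants who responded 'Very willing' were defined as vaccine willing". *Somewhat willing*, *Not willing* and *Don't know* thus share one category. No reason for the threshold is given.

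The 4-week item is not put to everyone: "participants who had not received an additional dose of the vaccine were asked, 'How willing are you to receive another COVID-19 vaccine dose". The same item is collected at baseline: "After enrollment, but before randomization into an intervention arm, participants were asked, 'How willing are you to receive another COVID-19 vaccine dose".

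The Statistical Analysis Plan section then says: "For the secondary outcome of vaccine willingness, we generated risk ratios using a Poisson regression model". On covariates: "The model for the overall effect estimation included the randomization arms and a term for the presence or absence of symptoms of anxiety or depression". Pre-trial willingness is not among them. The text supplied describes no ordered analysis, no second cut-point and no rule for *Don't know* other than counting it as not willing.

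Trial Design describes the target group as people "who show some willingness to vaccinate but remain hesitant about additional doses".

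**The concern.** Three features of the secondary analysis each limit what it can show.

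- **The cut.** Any effect confined to the lower levels is invisible. In a hesitant population shown a one-minute video, partial movement is a plausible effect.
- **The subset.** Whether a participant is asked depends on whether they were vaccinated after the intervention, which the intervention is meant to change. If those vaccinated come mainly from the most willing, an effective arm loses people from its own *Very willing* count.
- **The unused baseline.** Pre-trial willingness is likely to be the strongest predictor of the same item 4 weeks later, yet it has no stated use in the model.

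At stake is how a null willingness result is read. From the planned analysis alone, one could not separate no effect on willingness from an effect that the definition cannot register.

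**Working it through.** The plan has no figure to reproduce: the documents give no sample size, alpha, power, effect size or willingness distribution. The item levels, the cut, who is asked and the model terms come from the sections cited above. Everything else below is assumed: level shares, 200 per arm, odds ratio 1.5 and two-sided alpha 0.05. *Don't know* is left out because it has no place in the order.

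**1. What the cut can register.** The score is 1 for *Very willing* and 0 otherwise. Take Very/Somewhat/Not shares of 20/40/40% in control and 20/50/30% in an active arm. The risk ratio is 0.20/0.20 = 1 despite a 10-point difference in *Not willing*.

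**2. Information kept under proportional odds.** Information per participant on the log odds ratio, up to a common factor:

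- three-level ordinal: (1 − Σpᵢ³)/3
- *Very willing* cut: p₁(1 − p₁)

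| Very/Somewhat/Not (%) | Cut | Ordinal | Kept | Lost |
|---|---|---|---|---|
| 10/40/50 | 0.0900 | 0.2700 | 0.33 | 67% |
| 15/40/45 | 0.1275 | 0.2805 | 0.455 | about 55% |
| 25/40/35 | 0.1875 | 0.2925 | 0.64 | 36% |
| 35/35/30 | 0.2275 | 0.2958 | 0.77 | 23% |
| 50/30/20 | 0.2500 | 0.2800 | 0.89 | 11% |
| 60/30/10 | 0.2400 | 0.2520 | 0.95 | 5% |

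A grid with *Very* from 5% to 60%, *Somewhat* at least 10% and *Not* at least 5% gives losses from 3% (60/35/5) to 82% (5/50/45), with median 28%. The median describes the grid, not this trial.

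**3. Power under proportional odds (odds ratio 1.5, 200 per arm), cut versus ordinal.**

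- 10/40/50: 26% versus 57%
- 20/40/40: 40% versus 59%
- 30/40/30: 48% versus 59%
- 50/30/20: 52% versus 56%

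**4. When the effect is not proportional.** Simulation with 4,000 runs, 200 per arm and control shares 20/40/40; z-test on the cut versus Wilcoxon test.

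- 10 points from *Not* to *Somewhat* only: 5% (the alpha level) versus 33%
- 10 points from *Somewhat* to *Very* only: 63% versus 20%

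The ranking of the two analyses reverses with the shape of the effect.

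**5. The unvaccinated subset.** An invented illustration, per 100 participants, in which everyone vaccinated comes from *Very willing* and the vaccinated are left out of the outcome. Control: 20 very willing, 2 vaccinated, leaving 18/98 = 18.4%. Active: 24 very willing, 7 vaccinated, leaving 17/93 = 18.3%. The difference of 20 versus 24 disappears. Counting the vaccinated at or above *Very willing* restores it (18 + 2 = 20; 17 + 7 = 24). The text supplied does not say how the vaccinated are handled in this analysis.

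None of these figures gives the gain from the four-level outcome proposed under the fix. They concern the three-level item only.

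**The case against.** The strongest reply is that the cut is a reasonable choice. Stated willingness is a proxy for uptake, a strict threshold is conservative and easy to read, and it avoids ranking *Don't know*. People with some willingness may well start at *Somewhat willing*, and their next step up is the one the cut captures. Step 4 shows that the cut then beats an ordinal test, whereas steps 2 and 3 favour the ordinal analysis by assuming proportional odds.

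This stands as a reason to keep the cut. It does not settle where participants start: the eligibility criteria contain no willingness requirement, so people who are not willing can enrol. The reply also leaves the subset and the unused baseline untouched.

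Three further objections stand in part.

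- An ordered outcome with vaccination at the top mixes behaviour with intention and overlaps the primary outcome. It should therefore be supportive only.
- The plan is dated May 2, 2025, is written in the past tense and already mentions consistent results, so a new model would probably be post hoc.
- Sensitivity and imputation methods are placed in Appendices B and C, which were not available, so a related analysis there cannot be ruled out.

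A reader might infer that the cut throws away most of the information, or that it loses power exactly where the video should act. The documents support neither: they give no response distribution, and Trial Design does not say which step on the scale the video is expected to move. Nor does the plan score individual movement as no change. The outcome is status at 4 weeks, so no within-person change is scored in either direction.

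**Conclusion.** The point holds as a minor one about a secondary outcome. Three things follow from the text supplied: a *Not*-to-*Somewhat* difference between arms cannot register, the item is asked only in a post-randomization subset, and a collected baseline measure of the same item is left out of the model.

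The size of the information loss is undetermined, and it rests wholly on assumed shares and proportional odds. In the distributions tried it is large when few answer *Very willing* (44% at 20/40/40, 67% at 10/40/50) and modest when many do (5% to 17% where the share is 40% or more). The cut is not shown to be wrong, and a null result could not be blamed on it without the response distribution. The primary vaccination result is unaffected.

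**What to change.** 1. Keep the *Very willing* risk ratio as the plain summary, and add pre-trial willingness as a covariate. State how participants vaccinated by 4 weeks enter this analysis. Adjustment uses the baseline information but does not by itself undo selection into the unvaccinated subset.
2. Report the full four-option distribution by arm, with the number vaccinated beside it.
3. Add one supportive analysis in all randomized participants with 4-week status ordered as vaccinated > very willing > somewhat willing > not willing. Use proportional-odds regression with arm, symptom stratum and pre-trial willingness, and handle missing 4-week status by the plan's multiple imputation.
4. Place *Don't know* with *Somewhat willing*, then repeat with it placed with *Not willing*.
5. Label the analysis post hoc if results are already known.

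The cost is one added model, its repeat and a table, all on data already collected. The downside is a proportional-odds assumption spanning behaviour and intention, and an odds ratio that is harder to read than a risk ratio. If Appendix B or C already contains such an analysis, a cross-reference in the main text is enough for that part.
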